### ***Linked adverse events that worsened or became serious***

An AE that worsened or became serious will have a separate record in the data from the original event record with a reference identification number that links the new record to the original record. An AE that worsened or became serious will be considered a new recurring AE in the summary of recurrent events or in the summary of events by time intervals.

#### **2.5.5 Unscheduled visits**

Unscheduled visit measurements of laboratory data, vital signs, and ECG will not be included in the by-visit summaries, but will be used for computation of Baseline and PCSAs.

#### **2.5.6 Pooling of centers for statistical analyses**

Not applicable.

#### **2.5.7 Statistical technical issues**

Not applicable.

### **3 INTERIM ANALYSIS**

No interim analysis is planned.

## **4 DATABASE LOCK**

The database is planned to be locked approximately 4 to 6 weeks after last participant last visit.

## **5 SOFTWARE DOCUMENTATION**

All summaries and statistical analyses will be generated using SAS version 9.4 or higher.

## **7 LIST OF APPENDICES**

Appendix A: Efficacy Analysis SAS pseudo code

Appendix B: Criteria for Potentially Significant Abnormalities

Appendix C Diagram for Identifying Missing Data due to COVID-19

Appendix D Schedule of Activities

## Appendix A Efficacy Analysis SAS pseudo code

### Primary Analysis missing data imputation:

- 1) Multiple imputations in participants who have missing HbA1c values at Week 56

**Step 1:** Perform regression to estimate pooled mean and standard deviation of non-missing baseline HbA1c measures

```
proc glm data=BaseHbA1c;
    class ARM HbA1c_strata BMI_strata;
    model base = ARM HbA1c_strata BMI_strata;
    ods output FitStatistics=basefit;
run;

proc sql noprint;
    select RootMSE, depmean
    into :std, mean
    from basefit;
quit;
```

**Step 2:** For participants with missing HbA1C values at week 56, simulate week 56 HbA1c 10000 times by random draw (with seed=14829) from a normal distribution with mean equal to baseline HbA1c and STD equal to the pooled STD from the regression model in Step 1. In case baseline HbA1c is missing, pooled mean is used as baseline HbA1c. For participants with non-missing HbA1C values at week 56, repeat the same record 10000 times (iteration 1 to 10000) to generate 10000 data sets.

```
data HbA1cW56Complete;
  set InputData;
  call streaminit(14829);
  do _imputation_ = 1 to 10000;
    if base = . then newbase = &mean; /* in case of missing baseline HbA1c measure, pooled mean is used as the
baseline HbA1c*/
    else newbase = base ;

    base_simu = rand ('normal', newbase, &std);

    if aval=. then do ;
      aval=base_simu ;
      msfl = 'Y'; /* Flag missing record for tipping analysis */
    end;

    chg_wk56 = aval - newbase ;

    output ;
  end;
run;
```

**Step 3:** Use ANCOVA and Rubin's formula to obtain the between-group difference and 95% CI.

```
proc mixed data=HbA1cW56Complete;
  class ARM HbA1c_strata BMI_strata region;
  model chg_wk56 = ARM HbA1c_strata BMI_strata region NEWBASE;
  by _Imputation_;
```

```
lsmeans ARM/ pdiff=control ('Dulaglutide 1.5 mg') cl;  
ods output LSMeans=lsmeans diffs=lsmeansdiff;  
run;  
  
proc mianalyze parms=lsmeansdiff;  
modeffects ARM;  
by ARM;  
ods output parameterestimates=miparm;  
run;
```

In this sample SAS® (version 9.4) code:

- BaseHbA1c contains one observation per participant in the ITT population with Baseline HbA1c value.
- InputData contains one observation per participant in the ITT population with Week 56 HbA1c value
- HbA1cW56Complete is the final output containing 10,000 lines by participant with all observed and simulated data used for the ANCOVA.
- ARM is the randomized treatment group (Dulaglutide 1.5 mg, Efpeglenatide 4mg, Efpeglenatide 6mg).
- HbA1c\_strata is the randomization stratum of screening Hb1Ac (<8.0, ≥8.0%)
- BMI\_strata is the randomization stratum of BMI at Visit 3(<30, ≥30)
- BASE is the observed baseline HbA1c.
- BASE\_simu contains the simulated baseline HbA1c values.
- NEWBASE is the baseline HbA1c including observed (If non-missing) and imputed (If missing, pooled mean) data.
- CHG\_WK56 is the change from baseline in HbA1c at Week 56.
- REGION is the geographical region.
- The seed is 14829.

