##### **Primary Analysis:**

The statistical analysis for the primary endpoint is described below.

The Baseline value is defined in [Section 2.1.1](#).

Analysis of the primary efficacy endpoint (change from Baseline to Week 56 in HbA1c) will be performed using the ITT population, using HbA1c measurements obtained during the study, including those obtained after IMP discontinuation or introduction of rescue therapy.

The primary efficacy endpoint of change in HbA1c from Baseline to Week 56 will be analyzed with missing values imputed by BOCF-like MI method for both efpeglenatide and dulaglutide groups, under the MNAR framework:

- For participants with missing HbA1c values at Week 56, the missing values will be imputed using a random draw from a normal distribution with mean equal to their Baseline HbA1c and the standard deviation equal to the pooled standard deviation calculated from the square root of the mean square error estimated from a regression model with Baseline HbA1c as the dependent variable and randomization strata and treatment as the covariates.

In this analysis, missing endpoint values will be imputed 10 000 times to generate 10 000 data sets with complete data. Each of the complete datasets after the imputation will be analyzed by the ANCOVA model with the treatment groups (efpeglenatide 4 or 6 mg, dulaglutide 1.5 mg), randomization stratum of screening HbA1c ( $<8.0$ ,  $\geq 8.0\%$ ), Visit 3 (Day 1) BMI ( $<30$  and

$\geq 30 \text{ kg/m}^2$ ), and geographical region (North America, Eastern Europe (including Hungary and Poland)) as fixed effects, and baseline HbA1c value as a covariate.

In case a baseline value needed for multiple imputations is missing, it will be imputed by the population mean at Baseline.

SAS pseudo-codes are provided in [Appendix A](#).

Results from each complete dataset will be combined to provide the adjusted mean change in HbA1c from baseline to Week 56 (regardless of treatment discontinuation or initiation of rescue therapy) for each treatment group, as well as the between-group difference (comparing each efpeglenatide group versus dulaglutide group) and the 95% CI for the difference. This will be implemented using MIANALYZE procedure in SAS. If the UB of the 2-sided 95% CI for the adjusted mean difference (efpeglenatide versus dulaglutide) in HbA1c change from baseline to Week 56 is  $\leq 0.3\%$ , the noninferiority will be declared.

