## Step 2: Multiple imputations

### 1) Multiple imputations in participants who have missing HbA1c values at Week 56 not due to Covid-19

For participants with missing HbA1C values at week 56, simulate week 56 HbA1c 10000 times by random draw (with seed=14829) from a normal distribution with mean equal to baseline HbA1c and STD equal to the pooled STD from the regression model in Step 1. In case baseline HbA1c is missing, pooled mean is used as baseline HbA1c.

For participants with non-missing HbA1C values at week 56, repeat the same record 10000 times (iteration 1 to 10000) to generate 10000 data sets.

```
data data_OUT_MI_MISSING;
  set base_imputed (where W56_missing = "Y" and COVID = "N");
  call streaminit(14829);
  do _imputation_ = 1 to 10000;

    base_simu = rand ('normal', newbase, &std);

    if aval_W56=. then do ;
      aval_W56=base_simu ;
    end;

    chg_wk56 = aval_W56 - newbase ;

    output ;
  end;
run;
```

2) Multiple imputations in participants who have missing HbA1c values at Week 56 due to Covid-19

```
proc sort data=base_imputed out= data_IN_COVID;
    by ARM;
run;

proc mi data =data_IN_COVID out= monotone nimpute=10000 seed=14829;
    by ARM;
    where (W56_missing ne "Y" or (W56_missing = "Y" and COVID="Y"));
    mcmc chain=multiple impute=monotone
    var BASE AVAL_W12 AVAL_W30 AVAL_W43 AVAL_W56;
run;

proc mi data= monotone out= OUT_MI_MISSING_COVID nimpute=1 seed=14829;
    by ARM_imputation_;
    class HbA1c_strata BMI_strata;
    monotone reg ( / details);
    var HbA1c_strata BMI_strata BASE AVAL_W12 AVAL_W30 AVAL_W43 AVAL_W56;
run;

data data_OUT_MI_MISSING_COVID;
    set OUT_MI_MISSING_COVID;
    if W56_missing = "Y";
run;
```

3) Identifying observed values

```
data data_OUT_COMPL_MI;
  Set   base_imputed (where = (AVAL_W56^=));
        _imputation_=0;
  do i = 1 to 10 000;
        _imputation=_imputation+1;
  output;
  end;
run;
```

4) Combine imputation datasets and use ANCOVA and Rubin's formula to obtain the between-group difference and 95% CI.

```
data dataMI;
  set   data_OUT_MI_MISSING
        data_OUT_MI_MISSING_COVID
        data_OUT_COMPL_MI;
run;
```

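### The SAP Appendix A pseudo code, if its printed logic is kept, gives one imputation repeated 10 000 times and not the 10 000 draws the SAP text specifies; the COVID-19 model step also names the wrong data set

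*SAP*

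**What the plan says.** SAP 2.4.4.1 (Primary Analysis) sets the method. A missing Week 56 HbA1c is replaced by normal draws centred on the participant's own baseline, with the root mean square error of a baseline regression as SD. It states that "missing endpoint values will be imputed 10 000 times to generate 10 000 data sets with complete data". Each data set goes through the ANCOVA and the results are combined with MIANALYZE. For implementation, "SAS pseudo-codes are provided in" Appendix A.

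The Step 2 text in Appendix A agrees with the method: "simulate week 56 HbA1c 10000 times by random draw (with seed=14829) from a normal distribution with mean equal to baseline HbA1c". The code beneath it reads each participant's record once and loops 10 000 times. On each pass it draws `BASE_SIMU`, tests "if aval=. then do" and, where that is true, executes "aval=base_simu". It also sets `MSFL`, with the comment "Flag missing record for tipping analysis".

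The COVID-19 sensitivity block (for SAP 2.4.4.1.1) uses the same construction: "if aval_W56=. then do". It then stacks three data sets into `dataMI`, which its legend names as the ANCOVA input. Its Step 3 runs PROC MIXED on `HbA1cW56Complete`, the output of the primary block.

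On status, the appendix is headed pseudo code, and its legend opens "In this sample SAS® (version 9.4) code".

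**The concern.** The printed code and the text it illustrates give different analyses. The variable that records missingness is also the variable that is overwritten, so the loop can impute only once per participant. A program that keeps this delivers a single stochastic imputation fixed by seed 14829. The estimate, and the upper bound compared with 0.3, then carry random error that 10 000 draws exist to remove, and Rubin's variance loses its between-imputation part.

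SAP 2.4.4.2.2 and 2.4.4.4.2 apply the same imputation method to FPG, body weight and the Week 30 changes, so a shared macro would carry the error further.

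The COVID-19 defect is separate. A sensitivity analysis run on the primary data set returns the primary answer and could be mistaken for confirmation.

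**Working it through.** **Background figure.** The plan gives no figure for imputation noise. Its power statement (SAP 1.3: SD 1.1, 300 per arm, margin 0.3, true difference 0) reproduces: SE = 1.1 × √(2/300) = 0.0898; 0.3/0.0898 − 1.96 = 1.38; power 91.6% (91.5% with the t distribution), against 91% stated. The point does not depend on it.

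**Loop logic, one participant with AVAL missing.**
- Pass 1: the test is true and AVAL takes draw 1.
- Passes 2 to 10 000: a new `BASE_SIMU` is drawn, but AVAL is no longer missing, so the test is false and draw 1 is output again. AVAL is read before the loop and nothing resets it.
- Emulated over 10 000 passes with an input SD of 0.6: the printed logic gives 1 distinct value (SD 0). With AVAL reset on each pass there are 10 000 distinct values (SD 0.59).

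The retrieved-dropout and back-up code uses PROC MI and does not have this fault.

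**COVID-19 block.** Besides the data set name in Step 3, `CHG_WK56` is derived only for records missing for non-COVID reasons. Redirecting Step 3 to `dataMI` alone would leave the COVID-imputed records without a response. The observed records would also lack one unless it came in with the input data.

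**Size: assumptions.** The missing rate m, the imputation SD and the mITT size (SAP 2.3.1.2) are not in the documents. The range used is m = 5-20%, SD = 0.3-0.6 and n = 150-300 per arm. Anchors for the SD:
- Protocol 5.1 (I 05) limits screening HbA1c to 7.0-10.0%, with strata split at 8.0%. For a uniform spread within strata and a share p at or above 8.0%, SD = √[((1 − p) × 1² + p × 2²)/12]. This is 0.40 at p = 0.3 and 0.51 at p = 0.7.
- Simulated normal baselines limited to 7-10% gave about 0.30-0.44.
- Day 1 values can fall somewhat outside the screening limits, hence 0.6 at the top.

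**Seed noise.** 95% half-width in the difference from one draw per participant = 1.96 × SD × √(2m/n).

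| n per arm | m | SD | Half-width | Share of 0.3 |
|---|---|---|---|---|
| 300 | 5% | 0.3 | 0.011 | 4% |
| 300 | 10% | 0.5 | 0.025 | 8% |
| 300 | 20% | 0.6 | 0.043 | 14% |
| 150 | 20% | 0.6 | 0.061 | 20% |

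With 10 000 real draws each figure is divided by √10 000 = 100, giving 0.0001 to 0.0006.

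**Standard error.** ANCOVA simulation with three arms and a change SD of 1.0, single-draw SE against Rubin SE:
- 300 per arm, 10%, SD 0.5: 0.0830 against 0.0840 (1.2% low)
- 300 per arm, 20%, SD 0.6: 0.0844 against 0.0872 (3.2% low)
- 150 per arm, 20%, SD 0.6: 0.1196 against 0.1235 (3.2% low)

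Multiplied by 1.96, the SE gaps move the upper bound by 0.002 to 0.008. With SDs of 0.30-0.44 the shortfall was about 0.2-2%. At 300 per arm with SD 0.5-0.6, the single-draw SE (0.083-0.084) is not below the empirical SD of the estimate (0.080-0.081).

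**Tipping point, only if its program reuses these records.** One step of 0.1 in δ moves the difference by about 0.1 × m. At 10-20% missing, SD 0.4-0.6 and 150-300 per arm, the seed noise equals 1.96 × 0.4 × √(0.4/300)/0.02 = 1.4 to 1.96 × 0.6 × √(0.2/150)/0.01 = 4.3 steps.

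**The case against.** The strongest reply is that the governing text is right and the listing is only illustrative. As printed it would not run: there is no sort before the BY step on `_Imputation_`, the INTO clause lacks a colon and the MIANALYZE statement is misspelled. A programmer has to rework it with the correct prose alongside. This stands as a limit on the claim. A reader might infer that the trial's primary result rests on a single imputation, but the documents do not show the production program. The other repairs, however, do not touch the overwrite, which is valid syntax in a DATA step.

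A reader might also infer that the error would pass unseen. It need not: a between-imputation variance of zero is plain to anyone who inspects the MIANALYZE output.

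The COVID-19 analysis runs only if over ten participants lack the endpoint because of COVID-19 (SAP 2.4.4.1.1). If the primary data set is not available to that program, Step 3 fails visibly. Its legend already records the intended input. The irregular index names in that block may be losses in text conversion and are not counted here.

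SAP 2.5.4 accepts measurements within 30 days of Day 392, and the mITT definition drops many participants cut off by early termination. Both lower the missing fraction, which favours the lower part of the size range. Finally, no tipping-point code is printed beyond the `MSFL` flag, so inheritance of the fault there is conditional.

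**Conclusion.** Wrong as written. The Appendix A logic contradicts SAP 2.4.4.1 and the appendix's own Step 2 text. A program that keeps it after the other repairs performs one stochastic imputation copied 10 000 times, with zero between-imputation variance, in the primary block and again in the COVID-19 block for values missing for other reasons. If the COVID-19 analysis is triggered and the primary data set is available, its printed Step 3 would repeat the primary result and not test COVID-19 missingness.

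Under the assumed 5-20% missing and SD 0.3-0.6, the seed noise is about ±0.011 to 0.043 at 300 per arm and up to 0.061 at 150 per arm, or 4-20% of the margin. The SE is about 0.2-3% too small. This is avoidable noise that matters only when the upper bound lies near 0.3. A reader might infer bias or an inflated type I error; neither is shown, and at 300 per arm the simulated SE was not below the empirical spread.

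**What to change.** - In both loops, leave the source variable untouched. Write the value for each pass to a new variable, for example `aval_mi = coalesce(aval, base_simu);` (with `aval_W56` in the COVID-19 block). Set `MSFL` from the unchanged source variable in the primary loop, and compute `CHG_WK56` from the new variable.
- Sort by `_imputation_` before PROC MIXED and by ARM before MIANALYZE.
- In the COVID-19 block, derive `CHG_WK56` in all three stacked data sets, confirm that observed records are indexed 1 to 10 000, and run Step 3 on `dataMI`.
- Add a check that draws differ across `_imputation_`, so that the between-imputation variance is above zero whenever values are missing. Confirm that the production program, including any tipping-point code, does not copy the printed logic.

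The cost is a few lines in each of two blocks and one program check. The stated method does not change.

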**Sensitivity analysis using retrieved-dropout multiple imputation method:**

1. Multiple imputations in participants who prematurely discontinued the study treatment before the Week-56 visit:

```
proc mi data=data_IN out=data_OUT_DISC nimpute=10000 seed=14829;  
  where PEOT56FL = "Y";  
  by ARM;  
  var BASE AVAL_W56;  
  monotone regression (AVAL_W56= BASE );  
run;
```

2. Multiple imputations in participants who stay on the study treatment until the Week-56 visit:

```
proc mi data=data_IN out=data_OUT_COMPL_MI nimpute=10000 seed=14829;  
  where PEOT56FL='N';  
  by ARM;  
  class HbA1c_strata BMI_strata;  
  var HbA1c_strata BMI_strata base AVAL_W56;  
  monotone regression (AVAL_W56 = HbA1c_strata BMI_strata BASE );  
run;
```

3. Combine multiple imputations from the step 1 and step 2 above

```
Data dataMI;  
set data_OUT_DISC  
    data_OUT_COMPL_MI  
run;
```

**Back-up plan:**

```
proc mi data =data_IN out=data_OUT_MI nimpute=10000 seed=14829;  
  by ARM;  
  class HbA1c_strata BMI_strata;  
  var HbA1c_strata BMI_strata base AVAL_W56;  
  monotone regression (AVAL_W56 = HbA1c_strata BMI_strata BASE );  
run;
```

In this sample SAS® (version 9.4) code:

- DATA\_IN is the input dataset including one observation per participant in the ITT population with Baseline HbA1c value and change from baseline at Week 56.
- data\_OUT\_DISC is the output dataset including observed and imputed data for participants who have prematurely discontinued the treatment.
- data\_OUT\_COMPL\_MI is the output dataset including observed and imputed data for all participants who have completed the 56-week study treatment period.
- Data\_OUT\_MI is the output dataset including observed and imputed data for all participants using backup plan.
- PEOT56FL is the variable indicating whether the participant prematurely discontinued the study treatment (PEOT56FL="Y" if the participants prematurely discontinued the study treatment before Week 56 visit and PEOT56FL="N" if the participant stay on the study treatment until Week 56 visit).
- ARM is the randomized treatment group (Dulaglutide 1.5 mg, Efpeglenatide 4mg, Efpeglenatide 6mg).
- HbA1c\_strata is the randomization stratum of screening Hb1Ac (<8%, ≥8%)
- BMI\_strata is the randomization stratum of BMI at Visit 3(<30, ≥30)
- BASE is the baseline HbA1c.
- AVAL\_W56 is the HbA1c at Week 56.
- The seed (14829) has been chosen arbitrarily and is based on the study code (EFC14829).

**Sensitivity analysis** (*If more than 10 missing endpoint data impacted by COVID-19*):

**Step 1:** Perform regression to estimate pooled mean and standard deviation of non-missing baseline HbA1c measures

```
proc glm data=BaseHbA1c;
    class ARM HbA1c_strata BMI_strata;
    model base = ARM HbA1c_strata BMI_strata;
    ods output FitStatistics=basefit;
run;

proc sql noprint;
    select RootMSE, depmean
    into :std, mean
    from basefit;
quit;

data base_imputed;
    set InputData;
    if base = . then newbase = &mean; /* in case of missing baseline HbA1c measure, pooled mean is used as the
baseline HbA1c*/
    else newbase = base ;
run;
```

## Step 2: Multiple imputations

### 1) Multiple imputations in participants who have missing HbA1c values at Week 56 not due to Covid-19

For participants with missing HbA1C values at week 56, simulate week 56 HbA1c 10000 times by random draw (with seed=14829) from a normal distribution with mean equal to baseline HbA1c and STD equal to the pooled STD from the regression model in Step 1. In case baseline HbA1c is missing, pooled mean is used as baseline HbA1c.

For participants with non-missing HbA1C values at week 56, repeat the same record 10000 times (iteration 1 to 10000) to generate 10000 data sets.

```
data data_OUT_MI_MISSING;
  set base_imputed (where W56_missing = "Y" and COVID = "N");
  call streaminit(14829);
  do _imputation_ = 1 to 10000;

    base_simu = rand ('normal', newbase, &std);

    if aval_W56=. then do ;
      aval_W56=base_simu ;
    end;

    chg_wk56 = aval_W56 - newbase ;

    output ;
  end;
run;
```

2) Multiple imputations in participants who have missing HbA1c values at Week 56 due to Covid-19

```
proc sort data=base_imputed out= data_IN_COVID;
    by ARM;
run;

proc mi data =data_IN_COVID out= monotone nimpute=10000 seed=14829;
    by ARM;
    where (W56_missing ne "Y" or (W56_missing = "Y" and COVID="Y"));
    mcmc chain=multiple impute=monotone
    var BASE AVAL_W12 AVAL_W30 AVAL_W43 AVAL_W56;
run;

proc mi data= monotone out= OUT_MI_MISSING_COVID nimpute=1 seed=14829;
    by ARM_imputation_;
    class HbA1c_strata BMI_strata;
    monotone reg ( / details);
    var HbA1c_strata BMI_strata BASE AVAL_W12 AVAL_W30 AVAL_W43 AVAL_W56;
run;

data data_OUT_MI_MISSING_COVID;
    set OUT_MI_MISSING_COVID;
    if W56_missing = "Y";
run;
```

3) Identifying observed values

```
data data_OUT_COMPL_MI;
  Set   base_imputed (where = (AVAL_W56^=));
        _imputation_=0;
  do i = 1 to 10 000;
        _imputation=_imputation+1;
  output;
  end;
run;
```

4) Combine imputation datasets and use ANCOVA and Rubin's formula to obtain the between-group difference and 95% CI.

```
data dataMI;
  set   data_OUT_MI_MISSING
        data_OUT_MI_MISSING_COVID
        data_OUT_COMPL_MI;
run;
```

### Step 3: ANCOVA analysis

```
proc mixed data=HbA1cW56Complete;
  class ARM HbA1c_strata BMI_strata region;
  model chg_wk56 = ARM HbA1c_strata BMI_strata region NEWBASE;
  by _Imputation_;
  lsmeans ARM/ pdiff=control ('Dulaglutide 1.5 mg') cl;
  ods output LSMeans=lsmeans diffs=lsmeansdiff;
run;

proc mianalyze parms=lsmeansdiff;
  modeleffects ARM;
  by ARM;
  ods output parameterestimates=miparm;
run;
```

In this sample SAS® (version 9.4) code:

- BaseHbA1c contains one observation per participant in the ITT population with Baseline HbA1c value.
- InputData contains one observation per participant in the ITT population
- data\_OUT\_COMPL\_MI is the output dataset including observed values 10,000 times by participant
- data\_OUT\_MI\_MISSING is the output dataset containing 10,000 lines per participant with missing endpoint data not due to COVID-19
- data\_OUT\_MI\_MISSING\_COVID is the output dataset containing 10,000 lines per participant with missing endpoint data due to COVID-19
- dataMI is the final output containing 10,000 lines by participant with all observed and simulated data used for the ANCOVA.

- ARM is the randomized treatment group (Dulaglutide 1.5 mg, Efpeglenatide 4mg, Efpeglenatide 6mg).
- HbA1c\_strata is the randomization stratum of screening Hb1Ac (<8.0, ≥8.0%)
- BMI\_strata is the randomization stratum of BMI at Visit 3(<30, ≥30)
- BASE is the observed baseline HbA1c.
- BASE\_simu contains the simulated baseline HbA1c values.
- NEWBASE is the baseline HbA1c including observed (If non-missing) and imputed (If missing, pooled mean) data.
- CHG\_WK56 is the change from baseline in HbA1c at Week 56.
- W56\_missing = for each patient, “Y” if the Week 56 value is missing, otherwise W56\_missing = “N”.
- COVID = for each patient, “Y” if the missing data at Week 56 is impacted by COVID-19, otherwise COVID = “N”.
  - REGION is the geographical region.
  - The seed is 14829.

